6.2 Subject Withdrawal

At the end of the study subjects will be evaluated to determine if they completed all study procedures or if they were discontinued from the study early. If the subject discontinued at any point during the study, the primary reason for withdrawal should be recorded on the Study Conclusion page of the CRF by selecting one of the options below.

1. Subject did not meet study criteria
2. Adverse event
3. Subject lost to follow up
4. Protocol Violation
5. Withdrawal of informed consent
6. Other

Subjects may withdraw from the study at any time at their own request, or they may be withdrawn at any time at the discretion of the investigator or sponsor for safety or, behavioral reasons, or the inability of the subject to comply with the protocol-required schedule of study visits or procedures at a given study site.

The following circumstances require discontinuation of study treatment and/or premature subject withdrawal:

- Protocol violation that may impact the outcome of the subject's safety
- Withdrawal of informed consent
- Subject lost to follow-up
- Unblinding of the subject
- Pregnancy
- Death

If a subject is discontinued or prematurely withdraws from the study, reasons for discontinuation or withdrawal and associated date must be documented in the relevant section(s) of the CRF.

GlaxoSmithKline Consumer Healthcare Confidential

Template Version Effective: 22-Jun-2017

Page 36 of 61

Document Name	003208076tpcoloc.pdf	Document Identifier	Effective Date
Type	Version		
eldo_clinicalellbc	0.0. DIFFERENT MESSER Version CURRENT	1090032d580fb94bc	14-Aug-2017 09:06:22

Potassium Nitrate / Sodium Fluoride

208078

Final 1.0 Clinical Protocol

If a subject does not return for a scheduled visit, every effort should be made to contact the subject. The Investigator or site staff should attempt to contact the subject twice. After two attempts, clinical site staff must send a registered letter. If no response is received from the subject, the subject will be considered lost to follow up. All attempts to contact the subject and information received during contact attempts must be documented in the CRF. In any circumstance, every effort should be made to document subject outcome, if possible. The investigator should inquire about the reason for withdrawal, request that the subject return all study products (used and unused), and follow-up with the subject regarding any unresolved AEs.

It may be appropriate for the subject to return to the clinical site for final safety assessments. Subjects should be questioned regarding their reason for withdrawal. An OST may be conducted at the investigator's discretion.

Lack of completion of all or any of the early termination procedures will not be viewed as protocol deviations so long as the subject's safety was preserved.

If the subject withdraws from the study and also withdraws consent for disclosure of future information, no further evaluations should be performed and no additional data should be collected. The sponsor may retain and continue to use any data collected before such withdrawal of consent.

7 ASSESSMENTS

Every effort should be made to ensure that protocol-required tests and procedures are completed as described. However, it is anticipated that from time to time there may be circumstances, outside the control of the investigator that may make it unfeasible to perform the test. In these cases, the investigator must take all steps necessary to ensure the safety and well-being of the subject. When a protocol-required test cannot be performed, the investigator will document the reason for the missed test and any corrective and preventative actions that he or she has taken to ensure that required processes are adhered to as soon as possible. The study team must be informed of these incidents in a timely manner.

7.1 Efficacy

The following efficacy assessments will be performed at times defined in the [Study Procedures](#) section of this protocol.

7.1.1 Macpherson Modification of the Lobene Stain Index (MLSI)

Stain assessments will be performed by a single clinical examiner, in the same room with consistent light levels, throughout the study to facilitate standardization of the assessments. Subjects will brush their anterior teeth with a wetted toothbrush for 30 seconds prior to each stain assessment. Teeth will be air dried prior to the assessment, and during the assessment as needed.

GlaxoSmithKline Consumer Healthcare Confidential

Template Version Effective: 22-Jun-2017

Page 37 of 61

Document Name	098270B076ClinicalProtocol.pdf	Document Identifier	Effective Date
Type	Version		
eldo_clinicalProtocol	0.0. DIFFERENT MSLI Version CURRENT	1090032d580f8904c	14-Aug-2017 09:06:22

Potassium Nitrate / Sodium Fluoride

208078

Final 1.0 Clinical Protocol

The facial surfaces of each assessable tooth is divided into four regions. The ‘gingival’ region is defined as a crescent-shaped band, approximately 2 mm wide, adjacent to the free margin of the gingiva and extending to the crest of the interdental papillae of the adjacent teeth. The ‘body’ of the tooth is then sub-divided into three regions on the facial surfaces.

- **Maxillary and mandibular facial surfaces:** distal facial area; body facial area; mesial facial area

Extrinsic dental stain will be scored in each area using the MSLI [MacPherson, 2000], with grades of 0-3 assigned for each category of intensity and area.

Stain Intensity: intensity will be scored separately for the ‘gingival’ and ‘body’ areas of each assessable tooth as follows.

- Score 0 = No stain
- Score 1 = Light stain
- Score 2 = Moderate stain
- Score 3 = Heavy stain

Stain Area: area will be scored separately for the ‘gingival’ and ‘body’ areas of each assessable tooth as follows.

- Score 0 = No stain
- Score 1 = Stain covering up to 1/3 of region
- Score 2 = Stain covering up to 1/3 of region, and no more than 2/3 of region
- Score 3 = Stain covering more than 2/3 of region

7.1.1.1 Repeatability of the MSLI Assessment

To assess the repeatability of the stain assessments, replicate examinations will be performed by the same qualified dental examiner at each assessment visit. Five subjects will be randomly selected for repeat MSLI assessments across each assessment window (a total of 20 repeat MSLI assessments over the duration of the study). Every effort should be made to ensure the examiner does not refer to the results of the assessment completed prior to the repeat assessment. The results of the initial assessment will not be visible to the examiner or scribe when the repeat assessment is carried out.

7.1.2 Turesky Modification of the Quigley Hein Index Dental Plaque Assessment (TPI)

The qualified dental examiner must ensure that the subjects taking part in this exercise have been appropriately informed and have consented to take part to this activity.

GlaxoSmithKline Consumer Healthcare Confidential

Template Version Effective: 22-Jun-2017

Page 38 of 61

Document Name	003208076tprotocol.pdf	Document Identifier	Effective Date
Type	Version		
eldo_clinicalellbc	0.0. DIFFERENT MESSER Revision CURRENT	1090032d580f894bc	14-Aug-2017 09:06:22

Potassium Nitrate / Sodium Fluoride

208078

Final 1.0 Clinical Protocol

The dental examiner will use the Turesky Modification of the Quigley Hein Index [Turesky 1970], to assess plaque on all gradable teeth for the full mouth. Only natural teeth devoid of restorations which would prevent plaque grading can be assessed. This means no crowns, bridges, and teeth with restorations which, in the investigator's judgment would prevent an accurate grading. Wisdom teeth are not to be assessed.

The plaque will first be disclosed using a dye solution (provided by site). Subjects will then rinse with 5 millilitres (mL) of Trace Disclosing Agent for 10 seconds to disclose any residual plaque. They will expectorate and rinse with 10 mL of water for 10 seconds and expectorate again. Plaque will be assessed with each tooth being divided into 6 areas including the mesiofacial, facial, distofacial, mesiolingual, lingual and distolingual surfaces.

Disclosed plaque will be scored as follows and recorded in the CRF:

Score	Description
0	No plaque
1	Slight flecks of plaque at the cervical margin of the tooth
2	A thin continuous band of plaque (1 mm or smaller) at the cervical margin of the tooth
3	A band of plaque wider than 1 mm but covering less than 1/3 of the crown of the tooth
4	Plaque covering at least 1/3 but less than 2/3 of the crown of the tooth
5	Plaque covering 2/3 or more of the crown of the tooth

7.1.2.1 Repeatability of the Plaque Assessment

To assess the repeatability of the TPI assessments, replicate examinations will be performed by the same qualified dental examiner at each assessment visit. Five subjects will be randomly selected for repeat TPI examinations across each assessment window (a total of 10 repeat TPI examinations over the duration of the study). Repeatability assessments will be a minimum of 10 minutes between repeat plaque assessments of the same subject. The results of the initial assessment will not be visible to the examiner or scribe when the repeat assessment is carried out.

7.2 Safety

The following safety assessments will be performed at times defined in the [Study Procedures](#) section of this protocol.

GlaxoSmithKline Consumer Healthcare Confidential

Template Version Effective: 22-Jun-2017

Page 39 of 61

Document Name	003208076tpcolcol.pdf	Document Identifier	Effective Date
Type	Version		
eldo_clinicalellbc	0.0. DIFFERENT MESSER Version CURRENT	1090032d580fb94bc	14-Aug-2017 09:06:22

Potassium Nitrate / Sodium Fluoride

208078

Final 1.0 Clinical Protocol

7.2.1 Oral Soft Tissue (OST) Examination

Where possible, this procedure should be conducted by a single trained dental examiner. The examination will be accomplished by direct observation and palpation with retraction aids as appropriate. The examiner will include examination of the Labial Mucosa (including lips), Buccal Mucosa, and Mucogingival folds, Gingival Mucosa, Hard Palate, Soft Palate, Tonsilar Area, Pharyngeal Area, Tongue, Sublingual Area, Submandibular Area and Salivary Glands. The results of the examination will be recorded in the CRF as either normal or abnormal with details of any abnormalities. A brief description of any abnormality observed by the examiner or reported by the subject at the application site following and study procedures or administration of the treatment dentifrices will be recorded as an AE.

An OST examination will be conducted at each visit prior to any clinical assessments. While it is preferable to use the same OST examiner throughout the study, to facilitate subject flow, OST examinations may be carried out by different examiners.

7.2.2 Full Oral Hard Tissue (OHT) Examination

Where possible, this procedure should be conducted by a single dental examiner or clinically qualified designee for all subjects. Subjects with evidence of gross intraoral neglect or the need for extensive dental therapy will be excluded.

The OHT examination will assess grossly carious lesions or signs of erosive wear, enamel irregularities, tooth fracture, gross decay, decalcification and faulty restorations. Observations will be listed as "Absent" or "Present" and conditions noted as present will be described. Examination findings will be described and documented in the CRF. Any observation that changes from "Absent" to "Present" from the screening assessment must be recorded as an AE.

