
 To evaluate the ranking order in extrinsic dental stain removal, as measured by overall MLSI Area (A), of a 0.5% spherical silica dentifrice, a marketed 6% abrasive silica dentifrice, a 1% spherical silica / 5% STP dentifrice, and a marketed 16% abrasive silica / 5% STP dentifrice, after 2, 4 and 8 weeks twice daily brushing. 	
 Change from baseline in overall MLSI Area at 2, 4 and 8 weeks.

 To evaluate the ranking order in extrinsic dental stain removal, as measured by overall MLSI Intensity (I), of a low abrasivity 0.5% spherical silica dentifrice, a marketed low abrasivity dentifrice, a moderate abrasivity 1% spherical silica / 5% STP dentifrice, and a marketed higher 	
 Change from baseline in overall MLSI Intensity at 2, 4 and 8 weeks.

GlaxoSmithKline Consumer Healthcare Confidential

Template Version Effective: 22-Jun-2017

Page 19 of 61

Document Name	003270876tprotocol.pdf	Document Identifier	Effective Date
Type	Version		
eldo_clinicalelbc	0.0. DIFFERENT MESSAGING CURRENT	1090032d580fb904bc	14-Aug-2017 09:06:22

Potassium Nitrate / Sodium Fluoride

208078

Final 1.0 Clinical Protocol

abrasivity 5% STP whitening dentifrice, after 2, 4 and 8 weeks twice daily brushing.	
Safety	

 To evaluate the safety and oral tolerability of the test dentifrices when used twice daily for 8 weeks. 	
 Adverse Events

This is a POP study designed to look at the relative extrinsic dental stain and plaque removal performance for all test dentifrices. However, we would expect the following rank order in overall MLSI (A×I) to be observed: the 1% spherical silica / 5% STP dentifrice \geq 16% abrasive silica / 5% STP dentifrice \geq 0.5% spherical silica dentifrice \geq 6% abrasive silica dentifrice.

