6 STUDY PROCEDURES

6.1 Study Period

6.1.1 Screening - Visit 1

Subjects will be admitted to the clinical site at least 24 hours prior to Day 1 dosing.

The following procedures/assessments will take place in the order listed below (where possible), and recorded in the CRF:

- Obtain written informed consent. The investigator, or designee, must obtain written (signed and dated by the subject) informed consent from each subject participating in this study after adequate explanation of the aims, methods, objectives, and potential hazards of the study.

The investigator, or designee, must also explain to the subjects that they are completely free to refuse to enter the study or to withdraw from it at any time. Appropriate forms for documenting a written consent will be provided by the investigator or by GSK CH. The investigator, or designee, should sign and date the consent form to confirm that the consent process was completed correctly. The

GlaxoSmithKline Consumer Healthcare Confidential

Template Version Effective: 22-Jun-2017

Page 30 of 61

Document Name	003208076tpcofocal.pdf	Document Identifier	Effective Date
Type	Version		
eldo_clinicalelbc	0.0. DIFFERENT MESSAGING CURRENT	1090032d580f8944c	14-Aug-2017 09:06:22

Potassium Nitrate / Sodium Fluoride

208078

Final 1.0 Clinical Protocol

subject, will be provided with a copy of their signed and dated consent form and any other written information which they should be instructed to retain.

If, during a subject's participation in the study, any new information becomes available that may affect the subject's willingness to participate in the study, each ongoing subject should receive a copy of this new information and be re-consented into the study. Subjects will be provided with a copy of the signed and dated amended consent form. The date of consent will be recorded on the CRF.

- Collect demography and ethnicity.
- Collect medical history, including history of illegal drug, alcohol and tobacco use.
- Obtain complete medication history of all prescription or nonprescription drugs, and dietary and herbal supplements taken within 30 days prior to the planned first dose.
- Full oral soft tissue (OST) examination conducted by a qualified dental examiner.
- Full oral hard tissue (OHT) examination conducted by a qualified dental examiner.
- Visual MLSI stain assessment of the facial (maxillary and mandibular) surfaces by a qualified dental examiner.

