- Review Inclusion and Exclusion criteria. Pregnancy status will be confirmed verbally by the subject.
- Confirmation of subject eligibility.
- To prepare for study participation, instruct subjects on the use of the [Lifestyle Guidelines](#) and [Concomitant Treatment\(s\)](#) sections of the protocol.

6.1.2 Baseline MLSI Visit (Day 1) - Visit 2

Subjects will be admitted to the clinical site at least 24 hours following the Screening visit. Subjects will attend the study site having refrained from all oral hygiene procedures for at least 6 hours, and from eating and drinking for at least 2 hours (with the exception of water), prior to their scheduled visit.

The following procedures will be completed in the following order (where possible), and recorded in the CRF:

- Review changes in the subject's medical history including concomitant medication since Screening.
- Review of Inclusion Criteria 10, and Exclusion Criteria 12.b and e.
- Full OHT and OST examinations conducted by a medically qualified examiner. Record any changes since the Screening visit in the CRF.
- Confirm subject eligibility and continuance.
- Supervised brushing of the anterior teeth for 30 seconds using a wetted toothbrush, followed by flossing.
- Full MLSI stain assessment of the facial (maxillary and mandibular) teeth conducted by a qualified dental examiner.

GlaxoSmithKline Consumer Healthcare Confidential

Template Version Effective: 22-Jun-2017

Page 31 of 61

Document Name	003270B076tpctocol.pdf	Document Identifier	Effective Date
Type	Version		
eldo_clinicalelbc	0.0. DIFFERENT MESSAGING CURRENT	1090032d580fb904bc	14-Aug-2017 09:06:22

Potassium Nitrate / Sodium Fluoride

208078

Final 1.0 Clinical Protocol

- 4 eligible assessment teeth selected by a qualified dental examiner.
- Repeat full MLSI stain assessment of the 4 assessment teeth for selected subjects.
- Stratification (based on total MLSI score of the 4 facial surfaces of the 4 eligible assessment teeth).
- Unsupervised brushing with standard fluoride dentifrice.
- AEs and incidents. Assess symptoms by spontaneous reporting of adverse events and by asking the subjects to respond to a non-leading question such as “How do you feel?”

6.1.3 Baseline TPI Visit (Day 2) - Visit 3

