Subjects will be admitted to the clinical site 24 hours (+6, or -2 hours; including not brushing the evening before) after Visit 2, and will be requested to refrain from eating and drinking for at least 2 hours (with the exception of water), prior to their scheduled visit.

Prior to randomization the following procedures/assessments will be completed in the following order (where possible), and recorded in the CRF:

- Review changes in the subject's medical history including concomitant medication since the previous visit.
- Review of Inclusion Criteria 11.
- Confirmation of subject adherence and continuance. Full OST examination conducted by a medically qualified examiner.
- Subjects disclose plaque by rinsing with plaque disclosure solution.
- Pre-brushing full mouth TPI assessment of all gradable teeth, conducted by a qualified dental examiner.
- Randomization.

Following randomization, the following procedures/assessments will be completed in the following order (where possible), and recorded in the CRF:

- Dispense study dentifrice, toothbrush and diary/ instructions card.
- Supervised brushing with subject's allocated dentifrice. The time of brushing will be entered in the CRF.
- Subjects disclose plaque for a second time by rinsing with plaque disclosure solution.
- Post-brushing full mouth TPI assessment of all gradable teeth, conducted by a qualified dental examiner.
- Repeat TPI assessment conducted by a qualified dental examiner, for selected subjects.
- Post assessment brushing with standard fluoride dentifrice and toothbrush (if requested by the subject).

Document Name	003270B076tprotocol.pdf	Document Identifier	Effective Date
Type	Version		
eldo_clinicalellbc	0.0. DIFFERENT MESSER Revision CURRENT	1090032d580f8904c	14-Aug-2017 09:06:22

Potassium Nitrate / Sodium Fluoride

208078

Final 1.0 Clinical Protocol

- AEs and incidents captured. Assess symptoms by spontaneous reporting of adverse events and by asking the subjects to respond to a non-leading question such as “How do you feel?”

6.1.4 Day 15 (MLSI) - Visit 4

Subjects will be admitted to the clinical site having refrained from all oral hygiene procedures for at least 6 hours, and from eating and drinking for at least 2 hours (with the exception of water), prior to their scheduled visit.

The following procedures/assessments will be completed in the following order (where possible), and recorded in the CRF:

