Subjects will be admitted to the clinical site 24 hours (+6, or -2 hours; including not brushing the evening before) after Visit 2, and will be requested to refrain from eating and drinking for at least 2 hours (with the exception of water), prior to their scheduled visit.

The following procedures/assessments will be completed in the following order and recorded in the CRF:

- Subjects return study dentifrice, toothbrush, and diary card to the clinical site.
- Review changes in the subject’s medical history including concomitant medication since the previous visit.
- Review of completed diary to confirm timing of each brushing occasion in addition to missed/additional brushings.
- AEs and incidents captured. Assess symptoms by spontaneous reporting of adverse events and by asking the subjects to respond to a non-leading question such as “How do you feel?”
- Confirmation of subject adherence and continuance.
- Full OST conducted by a qualified dental examiner.
- Subjects disclose plaque by rinsing with plaque disclosure solution.
- Pre-brushing full mouth TPI assessment of all gradable teeth, conducted by a qualified dental examiner.
- Supervised brushing with subject’s allocated dentifrice.
- AEs and incidents captured following supervised brushing.
- Subjects disclose plaque for a second time by rinsing with plaque disclosure solution.
- Post-brushing full mouth TPI assessment of all gradable teeth, conducted by a qualified dental examiner.
- Repeat TPI assessment conducted by a qualified dental examiner.
- Post assessment brushing with standard fluoride dentifrice and toothbrush (if requested by the subject).
- AEs and incidents captured. Assess symptoms by spontaneous reporting of adverse events and by asking the subjects to respond to a non-leading question such as “How do you feel?”
- Study conclusion.

If a subject has any clinically significant, study-related abnormalities at the conclusion of a scheduled inpatient portion of the study, the GSK CH medical monitor (or designated representative) should be notified and depending on the abnormality, the subject may be asked

GlaxoSmithKline Consumer Healthcare Confidential

Template Version Effective: 22-Jun-2017

Page 35 of 61

 GlaxoSmithKline	Document Name	003208076tpcol.pdf	Document Identifier	Effective Date
	Type	Version		
	elido_clinicalelbc	0.0. DIFFERENT MESSAGING CURRENT	1090032d580fb904c	14-Aug-2017 09:06:22
	Reason For Issue	Auto Issue		

Potassium Nitrate / Sodium Fluoride

208078

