4.7 Analysis of Safety

4.7.1 Adverse Events and Serious Adverse Events

All summaries of safety will be performed using the safety population and will be analyzed based on treatment actually received. No formal statistical testing will be performed on summary comparisons related to safety related measurements.

All Aes will be coded using the medical dictionary for regulatory activities (MedDRA). Aes will be classified by system organ class (SOC) and by preferred term (PT). In addition, prior to database lock all Aes will be reviewed by the Clinical Research Director (or designee) and categorized as either oral or non-oral. Safety will be assessed based on any oral Aes (this includes those that are identified as treatment emergent oral soft tissue (OST) abnormalities and spontaneously reported oral Aes). Any new or worsening OST condition that occurs after the OST examinations at Screening will be recorded as an AE.

Aes will be summarized using descriptive statistics (frequency tables) by treatment group. Summary tables will indicate both the number of events and the number (percent) of subjects involved. Summaries of Aes will include only treatment emergent adverse events (TEAEs) unless otherwise noted. TEAEs are defined as new Aes that occur on or after the date/time of the first supervised use of the randomized treatment (or events aggravated in severity following treatment). Events with an onset date/time prior to first use of a treatment will be considered as non-treatment emergent. Listing of Aes (including non-treatment emergent from All Subjects) will be provided.

The following summary tables and listings will be presented by treatment group.

- Table of treatment emergent Aes by SOC and Preferred Term ([Table 14.3.1.1.1](#))
- Table of treatment emergent Aes by Oral/Non-Oral and Preferred Term ([Table 14.3.1.1.2](#))
- Table of treatment emergent treatment related Aes by SOC and Preferred Term ([Table 14.3.1.3.1](#))
- Table of Treatment emergent treatment related Aes by Oral/Non-Oral and Preferred Term ([Table 14.3.1.3.2](#))
- Table of Non-serious treatment emergent Aes by SOC and PT (only produced if there are more than 5 SAEs) ([Table 14.3.1.4](#))

GlaxoSmithKline Consumer Healthcare Confidential

Page 16 of 53

| | | | | |
|---|------------------|--|---------------------|----------------|
|  GlaxoSmithKline | Document Name | gsk-208078-reporting-and-analysis-plan.pdf | | |
| | Type | Version | Document Identifier | Effective Date |

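### Both scheduled oral hard tissue examinations precede first use of study product, so on the scheduled visits the rule in 7.2.2 that turns new findings into AEs covers only a pre-dose interval, and it conflicts with 6.1 and 8.2.1

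*Protocol*

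**What the plan says.** - **Objective.** Protocol section 2 gives the safety objective as "To evaluate the safety and oral tolerability of the test dentifrices when used twice daily for 8 weeks". The endpoint is adverse events.
- **The rule.** Section 7.2.2 sits under 7.2 Safety. The examination looks for gross caries or decay, erosive wear, irregular enamel, fracture, decalcification and defective restorations, each scored absent or present. A move from absent to present "from the screening assessment must be recorded as an AE".
- **When OHT is done.** At screening (6.1.1): "Full oral hard tissue (OHT) examination conducted by a qualified dental examiner". At Visit 2 (6.1.2): "Full OHT and OST examinations conducted by a medically qualified examiner. Record any changes since the Screening visit in the CRF". The Schedule of Activities shows the same two occasions.
- **When exposure starts.** At Visit 3 (6.1.3), after randomisation: "Dispense study dentifrice, toothbrush and diary/ instructions card". The supervised brushing follows, with the "allocated dentifrice. The time of brushing will be entered in the CRF".
- **What is examined later.** Visits 3 to 7 list an OST examination and no OHT. At end of treatment (6.1.7) the entry is "Full OST conducted by a qualified dental examiner".
- **AE window.** Under 8.2.1, collection starts with the standard-dentifrice brushing at Visit 2, or with the first disclosing rinse at Visit 3 for anyone who skips that brushing. Occurrences that begin after consent but before study treatment go to Medical History and not to the AE section.
- **Analysis.** SAP Amendment 4.7.1: "TEAEs are defined as new Aes that occur on or after the date/time of the first supervised use of the randomized treatment". The same sentence adds events that worsen after treatment. SAP 4.7.2 lists OST data (Listing 16.2.7.3), and protocol 10.2.4 also mentions OST data only. Neither text describes an OHT output.

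**The concern.** A mandatory AE trigger in the safety section should be able to operate while subjects are using the product. As scheduled, this one compares two examinations that are both complete before anyone has used a randomised paste. It also asks for an AE record at a point where 8.2.1 does not allow one, so site staff following both sections cannot comply with both.

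The gap matters more here than in most dentifrice studies. The four products share the same potassium nitrate level and nearly the same fluoride level, and differ mainly in abrasive system, with stated RDA from about 36 to about 166 (protocol 5.4). The introduction justifies the work by the wish to clean while limiting abrasive effect, particularly where dentine is exposed. Hard tissue is where an abrasive would act, yet it has no scheduled examination on treatment, while soft tissue is examined at every later visit. A report with no hard-tissue AEs could then be taken as a finding about the products when no one was scheduled to look.

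**Working it through.** The plan states no figure to reproduce, and the sample size basis is redacted and not needed. The check is a count of examinations against first use, followed by the size of what a Visit 7 examination could show.

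**1. Examinations against first use (protocol 6.1.1 to 6.1.7)**

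| Visit | Day | OHT | OST | Study product |
|---|---|---|---|---|
| 1 | screening | yes | yes | none |
| 2 | 1 | yes | yes | none |
| 3 | 2 | no | yes, before brushing | first use |
| 4 | 15 | no | yes | in use |
| 5 | 29 | no | yes | in use |
| 6 | 57 | no | yes | in use |
| 7 | 58 | no | yes | in use |

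OHT: 2 before first use, 0 on or after it. OST after the day of first use: 4. Time from first use to the last visit: 58 − 2 = 56 days.

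**2. The interval the rule can reach**

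Visit 2 falls 24 hours to 2 weeks after screening (protocol 4.4; SAP 3.3). On the scheduled visits, that is the only stretch over which an OHT change from screening can be seen.

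**3. The rule against the AE window**

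In 6.1.2 the OHT examination is listed before the standard-dentifrice brushing, so a change found there precedes either start of AE collection given in 8.2.1. It also precedes study treatment, so 8.2.1 assigns it to Medical History. Section 7.2.2 says it must be an AE. Both instructions cannot be followed.

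**4. What one OHT examination at Visit 7 could show**

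Take n = 30 evaluable per arm and 120 in all (protocol section 3). If no new finding is seen, the exact one-sided 95% upper limit is 1 − 0.05^(1/n):

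- per arm: 1 − 0.05^(1/30) = 9.5%
- all arms: 1 − 0.05^(1/120) = 2.5%

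The chance of at least one finding in an arm is 1 − (1 − p)^30. The documents give no value for p, so these rates are assumptions:

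| True rate p | Chance of at least one finding in 30 |
|---|---|
| 1% | 26% |
| 2% | 45% |
| 5% | 79% |
| 10% | 96% |

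**The case against.** The safety endpoint is adverse events, not OHT change, and hard-tissue events have other ways in. Subjects are asked a non-leading question at each treatment visit. Directly observed AEs must be reported (8.3). The AE definition covers conditions first detected after treatment (8.1.1). An examiner scores the assessment teeth at Visits 4 to 6 and every gradable tooth at Visit 7. Unplanned visits with extra assessments are allowed. All of this stands. A reader might infer that an on-treatment change can never be detected, or that the 8-week objective is wholly unanswered for enamel and dentine. The documents do not support either reading: a fracture or failed restoration could still be recorded.

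A reader might also infer that a hard-tissue finding can never be treatment-emergent, or that the trial will report zero such findings by construction. That goes too far as well. The SAP definition includes events that worsen after treatment, and its text plans no OHT output in which a zero would appear. The full list of displays is an attachment not available here.

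The instrument is coarse. It records gross conditions as absent or present and does not list dentine, so one later examination would not settle wear related to RDA. Both RDA extremes belong to marketed references. Test Product 1 (about 38) is 2 units above its reference (about 36), and Test Product 2 (about 58) is 108 below its reference (about 166). This limits what the fix can deliver, but does not explain an AE rule that stops before dosing.

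Finally, the Visit 2 examination comes just before eligibility is confirmed and the four assessment teeth are chosen, and Exclusion 14 concerns tooth condition. That is a real use for it. However, the criteria named for review at Visit 2 (Inclusion 10, Exclusions 12.b and 12.e) include no hard-tissue item, and a dental examiner scores the 12 anterior teeth before choosing four.

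**Conclusion.** The point holds in a limited form. On the scheduled visits, the 7.2.2 rule can apply only between screening and Visit 2, before any study product and before AE collection. It therefore conflicts with 6.1 and 8.2.1, and the three sections need reconciling whichever design is preferred. For 56 days of use, hard-tissue evidence in all four arms rests on incidental or self-reported AEs, against four scheduled soft-tissue examinations.

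The conclusion assumes that visits run in the listed order (6.1.2 says where possible) and that no unplanned OHT examination takes place. It does not touch the primary stain analysis. It does not show that any product harms hard tissue, nor that a repeat OHT examination would measure subtle abrasive wear or dentine loss. In an exploratory proof-of-principle study this is a correction worth making because it is cheap and removes a contradiction.

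**What to change.** **Preferred.** Move the second OHT examination from Visit 2 to Visit 7, beside the OST examination already done there. Amend the Schedule of Activities (Table 1-1 in the list of tables), 6.1.2 and 6.1.7. Add an OHT listing to the SAP beside Listing 16.2.7.3. The rule in 7.2.2 then compares screening with end of treatment and operates inside the AE window.

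**Cost.** Protocol wording and one listing, with the number of examinations unchanged. There would be no formal repeat hard-tissue check just before the assessment teeth are selected, so the examiner should apply Exclusion 14 during the Visit 2 MLSI assessment. The comparison would also span up to 15 days before first use (at most 14 from screening to Visit 2, plus 1 to Visit 3), so onset of a new finding needs to be judged and recorded.

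**If OHT stays at Visit 2 only.** State in 7.2.2 that it serves eligibility, remove the AE rule so that 7.2.2 agrees with 6.1 and 8.2.1, and say in the clinical study report that hard tissue was not systematically examined after exposure.

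Under the preferred option, the report should describe the Visit 7 result as a check for gross change only and give the upper limit (9.5% per arm if none is seen in 30).
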